***Traditional Intravenous Fluid versus Oral Fluid Administration in Primary
Total Knee Arthroplasty: A Randomized Trial***

Version 8.0 July 6th, 2017 - NCT03719378

Traditional Intravenous Fluid versus Oral Fluid Administration in Primary Total Knee Arthroplasty: A Randomized Trial

1. Purpose: Evidence-based guidelines on optimal perioperative fluid management have not been established in patients undergoing orthopaedic surgery. Typical intraoperative and post-operative fluid management has been arbitrary without evidence based guidelines established following total joint replacement. We have observed many patients post-operatively with side effects such as fluid overload leading to medical complications requiring either prolonged hospitalization or readmission. Additionally, this overload may lead to wound healing complications secondary to fluid shifts which may be devastating in this patient population. Recent randomized trials in major abdominal surgery suggest that large amounts of IV fluid may increase morbidity and hospital stay. Additionally, this increase fluid may be detrimental in patients with anastomosis leading to failure and/or complications in this patient population. We have defined to specific groups of interest to study in this patient population with regards to fluid management. The first group is the “traditional” IV fluid group where the anesthesiologist gives an unspecific amount of fluid intraoperatively and post-operatively the patient gets a set amount of fluid based on “protocol” on the orthopaedic floor (i.e. 75 cc/hour until good oral intake). This is the protocol utilized by most orthopaedic practices throughout the United States. The second group is defined as patients who are given a specific protocol preoperatively to optimize hydration, followed by limited fluids intraoperatively based on physiologic parameters. This study will investigate the effects of two regimens of intraoperative fluid management (“traditional” vs. “oral”) with physiologic and patient function as primary outcome measures after surgery.

2. Procedures:

- Patients meeting the inclusion criteria who are schedule for unilateral primary TKA will be identified.
- The patients will be approached regarding the study (in clinic by research staff) and if the patient is agreeable, informed consent will be obtained.

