- The patients will be randomized into the traditional vs. oral treatment groups (see below for details and protocol). The protocol for each group will be placed in sealed envelopes, 65 for each group, and picked randomly for each patient.
- The patients will attend their normal preoperative visits with the surgical team as well as their regularly scheduled preoperative clearance visit with the medical doctor (Surgery Welcome Center)
- Standard preoperative labs will be obtained (hematocrit, basic metabolic panel), at their preoperative appointment
- Additional preoperative labs will include urine specific gravity to monitor patient hydration which will be obtained the morning of surgery; this will be paid for by the CJR research fund.
- Standard laboratory values (hematocrit and basic metabolic panel) will be obtained postoperative day #1 and #2, if the patient has not been discharged.
- Urine output will be monitored on postoperative day #1 and #2 which is standard protocol
- Additional test will include urine specific gravity on postoperative day #1 and #2 as a marker of hydration as long as the patient is still in the hospital. If the patient is discharged postoperative day #1 we will collect this once in the morning, and once more before they are discharged. Payment of the cost of these laboratory evaluations will come from CJR research funds.
- Patients are encouraged to attend physical therapy 2-3 times a week for 6 weeks. Physical therapy log is attached with ROM and Girth measurement collected once a week for 4 weeks.
- Hematocrit, basic metabolic panel and urine specific gravity 2 weeks postoperatively at their routine follow-up visit will also be obtained. The cost of these laboratory tests will come from CJR research funding.
- Sixty-five patients in each group will be recruited for this study (see stats for power analysis). We will increase our number of enrollment to 75 in each group to account for patients that drop out and withdrawals from the study.

Traditional Fluid Protocol

- NPO Clears and Food after midnight.
- 2 Liters of lactated ringers administered by anesthesia intraoperatively.
- Postoperatively - 2 Liters of Crystalloid while in PACU and Inpatient Room for a Total of 4 Liters of Crystalloid within 24 hours.
 - Patient will receive 500 milliliters while in PACU and 1500 milliliters while in their Inpatient Room, for a total of 2 Liters.

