- Patients between the ages of 18-75 years old undergoing a primary total knee arthroplasty for a diagnosis of degenerative osteoarthritis who do not meet the exclusion criteria listed below.

EXCLUSION – patients will be screened for the following exclusion criteria at their routine preoperative appointment with the orthopaedic and internal medicine teams.

- Volume-dependent cardiac conditions:
- Aortic stenosis
- Pulmonary valve stenosis
- Subaortic stenosis
- Severe Aortic Insufficiency
- Chronic systolic heart failure
- Eisenmeinger Syndrome
- Severe pulmonary HTN
- Chronic or paroxysmal dysrhythmias
- Pre-operative electrolyte abnormalities
- Abnormalities of the HPA (hypothalamic-pituitary axis)
- Stage 3 Chronic Kidney Disease (or worse)
- Patients taking angiotensin receptor blockers (ARB)
- Patients with uncontrolled diabetes mellitus (patient with A1C of 7+ or on insulin)
- Patients whose BMI is > 38 or < 19

- Current use of long acting narcotic medication or 3 or more months of daily short acting narcotic medication
- Patients at risk for electrolyte abnormalities, dehydration or intra-operative hypotension. (patients taking angiotensin receptor blockers, ACE inhibitors (48 hours prior to surgery) and Diuretics)
- Patients with severe, untreated or uncontrolled GERD.
- Patients that cannot receive spinal anesthesia (e.g. patient with back fusions)
- Pre-Operative Anemia (pre op HCT <30%)

7. Treatment/Intervention Schedules or in the case of observational studies:

- As per section #2

8. Data Collection Procedures

- Preoperative history and physical will be performed as usual by the surgeon and/or their physician assistant. The patient will also be evaluated preoperatively (per standard procedure) by the general medicine team as well.
- Please refer to section 2 and 8 for the outcome measures, how they will be collected and the time intervals designated.
- Data will be stored on a password protected Microsoft Excel spreadsheet on a Centura approved secure computer.
- All data collected will be de-identified.

9. Methods of Evaluation

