10. Trial Design

- Please refer to the above sections regarding the discussion of the research study
- Patients will be identified based on the inclusion and exclusion criteria stated above. The patients will then be randomized into the “traditional” vs. oral arms of the study. Outside of the amount of preoperative, intraoperative and postoperative fluids given to the patients, there is no difference in the treatment or outcome measures between the 2 groups.

11. Statistical calculations- please refer to section 10, methods of evaluation

12. Confidentiality of the data.

- Data will be collected on a password protected excel spreadsheet that will be stored on a Centura password protected computer.
- All data collected will be de-identified.

Data sharing.

With whom will *identifiable* (contains any of the 18 identifiers) data be shared outside the immediate research team? For all that apply, explain confidentiality measures. Include data use agreements, if any.

Data will be shared with:		Name/Description/s
	No one	
	Coordinating Center	
	Statisticians	
x	Other researchers	[name]; [name]; [name]; [name], , [name], [name] (research coordinator), [name] (research data entry clerk), [name] (clinical research associate).
	Registries	
	Sponsor/s	
	External labs for additional testing	
	Journals	
	Publicly available dataset	
	Other	

Data security for storage and transmission. Include all that apply.

For electronic data stored on a desk top computer:

 Secure network	 Password access	 Data encryption	 Password protected file(s)
 Other comparable safeguard (describe):		Data will be de-identified	

For portable computing devices/external storage devices (e.g. laptop computer, PDA, CDs, memory sticks):

 Power-on password	 Data encryption
 Automatic log-off	 Password protected file(s)
 Other comparable safeguard (describe): Data will be de-identified	

For hardcopy data (including human biological specimens, CDs, tapes, etc.):

 Data de-identified by research team (stripped of the 18 identifiers)	 Locked suite or office

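### Sections 2 and 6 conflict with Section 10 on whether eligibility is complete before allocation, and no rule covers patients found ineligible afterwards

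*Combined protocol and SAP*

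**What the plan says.** Section 2 (Procedures) lists its opening steps in this order:

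1. "Patients meeting the inclusion criteria who are schedule for unilateral primary TKA will be identified".
2. "The patients will be approached regarding the study (in clinic by research staff) and if the patient is agreeable, informed consent will be obtained".
3. "The patients will be randomized into the traditional vs. oral treatment groups". On the mechanism: "The protocol for each group will be placed in sealed envelopes, 65 for each group, and picked randomly for each patient".
4. Patients attend the usual surgical visits and the medical clearance visit.
5. "Standard preoperative labs will be obtained (hematocrit, basic metabolic panel), at their preoperative appointment".

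Section 7 sets out no schedule of its own and refers back to Section 2.

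The Patient Selection Criteria, placed under Section 6, say of the exclusions that "patients will be screened for the following exclusion criteria at their routine preoperative appointment with the orthopaedic and internal medicine teams". The inclusion criterion just above adds that a patient must not meet any of those exclusions.

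Section 10 (Trial Design) says: "Patients will be identified based on the inclusion and exclusion criteria stated above". Its next sentence has patients randomised after that.

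The withdrawal paragraph at the end of Section 2 deletes the data of subjects who decide to leave the study. Section 2 also raises enrolment from 65 to 75 per group, to cover drop-outs and withdrawals.

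**The concern.** Randomisation protects the comparison only if the decision on who belongs in the trial cannot depend on the arm. If the envelope is open before medical review and blood results are in, a clinician who knows the allocation is deciding whether the patient stays. The arms are far apart: 4 litres of crystalloid against at most 500 ml of intravenous fluid. A borderline electrolyte result or a history of reflux could therefore be weighed differently according to the arm. Removing such patients would leave groups that differ for reasons other than treatment.

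Baseline measurements raise a related problem. Section 2 places the timed up and go and sit-to-stand tests at the preoperative appointment, carried out by research staff. If that appointment follows the draw, they may be recorded with the arm known.

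**Working it through.** No figure in the plan bears on the order of events, so the check compares the sections and adds two short pieces of arithmetic.

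**1. Order of eligibility and allocation**

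| Place | Order implied |
|---|---|
| Section 2, list order | inclusion criteria, consent, envelope, clearance visit, blood tests |
| Section 6, exclusions | screened at the preoperative appointment with both teams |
| Section 6, inclusion criterion | no exclusion may apply; timing of confirmation not given |
| Section 10 | inclusion and exclusion criteria, then randomisation |

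The first two rows together put part of the exclusion screening after the draw. The last row puts all of it before.

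**2. Which exclusions depend on the later steps**

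- Hematocrit below 30% needs the hematocrit.
- Electrolyte abnormalities need the metabolic panel, and no cut-off is given.
- Severe, untreated or uncontrolled GERD needs a clinical judgement.
- Cardiac diagnoses, BMI, insulin use, ARB use, narcotic use and back fusion can mostly be known from history or at an orthopaedic visit. Stage 3 kidney disease may already be on record.

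The exposed set is therefore a minority of the list, but it is not empty.

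**3. Is the arm known once the envelope is open?** Yes. The envelope holds the group's protocol, and no blinding is described for any role.

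**4. Is there a rule for ineligibility found after allocation?** None was found. The withdrawal paragraph covers a subject's own decision to leave. Section 9 names t-tests, regression and matching but defines no analysis population. Section 5 provides for a quarterly independent review that includes the inclusion and exclusion criteria, so ineligibility can come to light after allocation whatever the visit order.

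**5. The enrolment allowance.** Inputs from Section 2: 65 needed and 75 enrolled per group.

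- Tolerated loss = (75 − 65)/75 = 10/75 = 13.3% per group.
- Check: 75 × (1 − 0.133) = 65.

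The stated purpose is drop-outs and withdrawals. Any patient excluded after allocation draws on the same 10 places. The documents give no screen-failure rate, so the number used this way cannot be estimated.

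**6. ACE-inhibitor timing.** The oral regimen in Section 2 covers each of the 3 days before surgery, so that arm must be known about 3 × 24 = 72 hours ahead. The exclusion list attaches 48 hours before surgery to ACE inhibitors. If that refers to use at 48 hours, the item is settled about 72 − 48 = 24 hours after the oral arm has to be known. Reordering the visits would not close this gap.

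**The case against.** The strongest reply is that Section 2 is not labelled a timeline and its bullets are not strictly chronological. Six weeks of physical therapy comes before the 2-week blood tests, and the recruitment total comes last. Section 10 states the proper order explicitly. The inclusion criterion already contains the exclusions, so a site could follow Section 2's first step literally and still screen everyone before the draw. The exclusions are screened partly by the orthopaedic team, and that part could happen at the same clinic visit as consent.

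Much of this stands. The order in Section 2 is an inference from its list. A reader might conclude that the plan randomises patients in clinic before they are screened, but the documents do not support that: the clinic setting describes where patients are approached, and no place or date is given for the draw.

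The reply does not remove the conflict. Section 7 makes Section 2 the schedule, and the list is broadly chronological from consent through surgery to follow-up. Medical clearance and blood tests come after the draw in it. The inclusion criterion says what must be true of a patient, without saying when it is confirmed.

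A reader might also take the exclusion for risk of dehydration or intraoperative hypotension as open clinical judgement. Its parenthesis lists ARBs, ACE inhibitors and diuretics, which makes it largely a medication check, so it adds little to the concern.

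**Conclusion.** The point holds as an inconsistency with a gap. Sections 2 and 6, read in listed order, allow some exclusions to be applied after the arm is known, while Section 10 does not. Nothing in the plan says how a patient found ineligible after allocation is reported or analysed. The finding assumes that a site would treat Section 2 as its working sequence. Section 7 makes that reasonable but not certain.

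The size and direction of any bias cannot be computed. A reader might infer that a substantial share of patients would be lost at clearance, that the groups would fall below 65, or that an arm mean would shift by a given fraction of a standard deviation. Each needs an exclusion rate, an imbalance between arms and an outcome difference that the documents do not supply. The only supported figure is the 13.3% allowance, none of which is set aside for exclusions after allocation.

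The correction is worth making because it is cheap and protects the randomised comparison.

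**What to change.** - Reorder Section 2 to match Section 10: consent; clearance visit, blood tests and baseline tests; a dated record that each exclusion has been checked; then the envelope. Keep the draw early enough for the 3-day oral regimen to start.
- State that any patient found ineligible after allocation is reported and analysed in the assigned arm. Patients kept in this way do not use up the enrolment allowance unless their outcomes are missing.
- Reconcile the 48-hour ACE-inhibitor item with the 3-day regimen, so that it is clear when that item is judged relative to allocation. The choice is for the clinical team.

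The cost is protocol wording and a later envelope draw, with no extra visit or test. The small downside is that patients learn their arm closer to surgery. The documents do not give the interval between clearance and surgery, so the sponsor should confirm that it leaves room for the draw and the oral regimen.

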Based on my reading of the fluid management protocol, the study evaluates the hypothesis that the euvoolemia regimen leads to better outcomes than the traditional regimen. The former corresponds to the treatment group and the latter to the control group for the analysis, and assuming that the two groups demonstrate similarities in terms of potential pre-treatment confounding variables, such as measures obtained from preoperative history and physical, a comparison of post-treatment outcomes seems appropriate (e.g., t-tests). Even under random assignment to treatment, checks can be performed to ensure effective equivalence of confounders across treatment and control groups, an essential step in the case of small samples. If the results of such checks reveal potential confounding, including control variables in the analysis may be appropriate (e.g., in a linear regression) or a matching design to generate treatment-control pairs can be used.

While I do not have any substantive training in this field, it seems that some of the outcomes listed in the Procedures: Primary Outcomes section of the protocol may be mediated by others. For example, the association between receiving the treatment and readmission or length of hospitalization may be mediated by some of the other outcomes listed. Are there any known or suspected mediators at this point, either from the list of outcomes or beyond?

Concerning statistical power, in the figure below I calculate power (y-axis) for a range of hypothesised values of estimated effect sizes (colored lines), sample sizes per treatment and control group (x-axis), and arbitrarily chosen levels of significance (α) across the panels. Regarding α , I start with 0.05 and then make an adjustment based on an arbitrary number of hypotheses to be evaluated (eight, in this demonstration). The solid horizontal line at 0.8 represents the commonly accepted power value. As an example from Figure 1(b), for a medium-high effect size of 0.6 (green line) and evaluating eight hypotheses, in order to achieve power of 0.8 would require approximately 65 participants in each of the treatment and control groups.

[figure not shown]

Figure 1: Power calculations for hypothetical effect sizes and sample sizes (per group) at given values of α . The left panel uses $\alpha = 0.05$ and the right panel employs a Bonferroni correction for multiple hypotheses. In this case, evaluating eight hypotheses with a desired α of 0.05 yields an adjusted α of 0.00625.

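### Section 9 uses baseline values only after an undefined balance check; for outcomes with a clean preoperative value, prespecified ANCOVA would usually gain precision for one degree of freedom

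*Combined protocol and SAP*

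**What the plan says.** Section 9 (Methods of Evaluation) is the only analysis text; section 11 merely refers back to it. Its wording is advisory. Provided the arms resemble each other on pre-treatment variables, "a comparison of post-treatment outcomes seems appropriate (e.g., t-tests"). Balance checks are described as something that can be done. Then: "If the results of such checks reveal potential confounding, including control variables in the analysis may be appropriate", with linear regression as the example, "or a matching design to generate treatment-control pairs can be used". The variables to check are given only by illustration: "such as measures obtained from preoperative history and physical". Section 9 gives no threshold, no covariate list and no rule for choosing between regression and matching. It does not name the baseline value of an outcome as a covariate.

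The sample size comes from the same section. For effect size 0.6 and eight hypotheses at a Bonferroni alpha of 0.00625, "in order to achieve power of 0.8 would require approximately 65 participants in each of the treatment and control groups".

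Under Primary Outcomes in section 2, a preoperative value is scheduled for range of motion (B), girth (C), TUG and sit-to-stand (H), KSS/KOOS/VR-12 (N) and bioimpedance (Q). For bloods, section 2 states: "Standard preoperative labs will be obtained (hematocrit, basic metabolic panel), at their preoperative appointment". Quadriceps strength (G) and pain VAS (J) have no listed preoperative value. Body weight (A) is first measured in the holding area on the day of surgery, when the oral arm has already been drinking for three days.

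**The concern.** For a continuous outcome measured before and after surgery, the baseline usually explains part of the follow-up variance. Adjusting for it in every case, by a rule fixed in advance, recovers that precision. Adjusting only when the arms happen to differ recovers part of it, and how much depends on a trigger that section 9 does not define. With no fixed rule, the same outcome could be reported from a t-test, a regression or matched pairs, chosen once the data are visible.

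Timing limits how the remedy can be applied. The oral arm's intervention starts three days before surgery, so a value taken after that may already carry a treatment effect. No section dates the preoperative visit against the start of drinking. The documents also disagree on whether randomisation comes before or after that visit.

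**Working it through.** **Inputs from section 9.** Effect size d = 0.6 (SD 1), alpha = 0.05/8 = 0.00625, target power 0.80, n = 65 per arm. Sidedness is not stated, so both are shown. The correlation r between baseline and outcome is not given; I assume 0.3, 0.5 and 0.7.

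**The plan's figure.** Two-sample t-test by the noncentral t, noncentrality d × sqrt(n/2) = 0.6 × sqrt(32.5) = 3.42, 128 df.
- One-sided: 64 per arm gives 80% power, and power at 65 is 0.811. This reproduces the stated figure.
- Two-sided: critical t 2.780, 73 per arm needed, power at 65 is 0.738.

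**ANCOVA.** The variance is multiplied by (1 − r²) × (1 + 1/(2n − 4)), the second term allowing for chance baseline imbalance; df = 2n − 3 = 127. At r = 0.5 the factor is 0.75 × (1 + 1/126) = 0.756, and the noncentrality is 3.42/sqrt(0.756) = 3.93.

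| r | variance factor | power, two-sided | power, one-sided | n per arm for 80%, two-sided / one-sided |
|---|---|---|---|---|
| t-test | 1 | 0.738 | 0.811 | 73 / 64 |
| 0 | 1.008 | 0.733 | 0.807 | 74 / 65 |
| 0.3 | 0.917 | 0.784 | 0.848 | 68 / 59 |
| 0.5 | 0.756 | 0.873 | 0.917 | 56 / 49 |
| 0.7 | 0.514 | 0.975 | 0.987 | 39 / 34 |

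Break-even is at |r| of about 0.09.

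**Incomplete baselines.** Suppose half the patients, unrelated to arm or outcome, have a usable value and the rest receive the pooled mean. The covariate then explains about r²/2, so the factor is (1 − r²/2) × (1 + 1/126) = 0.963, 0.882, 0.761. Two-sided power is about 0.76, 0.80, 0.87.

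**Adjusting only when triggered.** The triggers below are my illustrations, applied to a single baseline covariate. Simulated two-sided power, 200,000 trials per scenario:

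| rule | r = 0.3 | r = 0.5 | r = 0.7 |
|---|---|---|---|
| baseline p < 0.05 | 0.740 | 0.749 | 0.759 |
| baseline p < 0.20 | 0.748 | 0.775 | 0.810 |
| standardised difference > 0.2 | 0.751 | 0.784 | 0.825 |
| standardised difference > 0.1 | 0.765 | 0.825 | 0.899 |
| always ANCOVA | 0.782 | 0.874 | 0.976 |

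Type I error, simulated for the p < 0.05 and > 0.1 rules, was 0.0029 to 0.0057, below 0.00625.

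**Why the baseline date matters.** If treatment has already shifted the baseline by an assumed 0.1 to 0.2 SD in the direction of the effect, ANCOVA at r = 0.5 estimates a true 0.6 as 0.6 − 0.5 × 0.1 = 0.55 down to 0.6 − 0.5 × 0.2 = 0.50. The same applies to an effort-dependent or self-reported baseline shifted by knowledge of allocation.

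**When the baseline is taken.** Section 2 lists "The patients will be randomized into the traditional vs. oral treatment groups" ahead of "The patients will attend their normal preoperative visits with the surgical team". Patient Selection Criteria, however, places exclusion screening at the routine preoperative appointment, and section 10 has eligible patients identified and then randomised. The first order puts the baseline after allocation; the second suggests it comes before.

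**The case against.** The strongest reply is that this is a preference for efficiency. The t-test is valid, section 9 already allows regression, the correlations are assumed, and the effect size is a demonstration value tied to no outcome. At r = 0.3 the gain is only about five points. The fix reaches five of 20 listed items and leaves out body weight, which is listed first. All of that stands and limits the size of the point. It does not remove it: baseline data already scheduled would go unused by default, and the method would stay unfixed.

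Three further objections change what can be claimed or proposed:
- The triggers simulated are not the plan's rule. Section 9 mentions history and physical measures, and even then only as an option. A reader might infer that the plan recovers some particular share of the ANCOVA gain; the documents fix no such share.
- Requiring ANCOVA at every scheduled visit would write in about 50 tests (range of motion 6, girth 4 sites × 6 = 24, TUG 2, sit-to-stand 2, patient-reported 3 × 2 = 6, bioimpedance 4, hematocrit 3, metabolic panel at least 3), against eight in the power calculation. The fix must not do this.
- If allocation was known when an effort-dependent or self-reported baseline was taken, adjustment could bias a comparison that was valid without it. The fix needs a stated consequence for that case.

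A reader might also infer from the order of section 2 that baselines follow randomisation. Patient Selection Criteria and section 10 point the other way, so the documents conflict and neither order is established.

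**Conclusion.** The point holds as a conditional gain in precision, together with a method left open. For continuous outcomes with a clean preoperative value, always-ANCOVA at 65 per arm raises two-sided power from 0.74 to about 0.78/0.87/0.98 at r = 0.3/0.5/0.7 (one-sided, 0.81 to 0.85/0.92/0.99). This rests on assumed correlations and on nearly all patients having a usable baseline; with half, two-sided power is about 0.76/0.80/0.87. If |r| is below about 0.09 there is nothing to gain.

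Two stronger readings are not supported. One is that the planned analysis is biased or inflates type I error: randomisation makes the t-test valid, and the two illustrative check-then-adjust rules tested under the null were conservative. This says nothing about choosing freely among methods after seeing results, which was not quantified. The other is that ANCOVA is better for every outcome: several have no preoperative value, or only one taken after drinking has begun. The change is worth making but is not critical; confidence in the size of the gain is medium.

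**What to change.** In section 9, replace the balance-check trigger and the matching option with: *Continuous outcomes with a preoperative value are compared between arms by ANCOVA, with treatment and that value as covariates, regardless of observed balance. Baseline tables are descriptive.*

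Add these conditions:
- Apply the model to whichever outcomes and visits the plan chooses to test. It adds no tests, and the allocation of alpha is a separate matter.
- Use a preoperative value only if its recorded date precedes the start of the oral arm's three days of drinking, with the same cut-off relative to surgery in both arms.
- For range of motion, TUG, sit-to-stand and KSS/KOOS/VR-12, also require that the value was taken before allocation was known. Otherwise keep the unadjusted comparison for that outcome.
- Keep patients without a usable value in the analysis, with the pooled mean of both arms as their covariate value.
- Do not adjust for holding-area weight, morning-of-surgery urine specific gravity or Preoperative Care Unit blood pressure, all taken after drinking starts.
- Treat range of motion and girth on postoperative days 1 and 2 as descriptive, because they exist only for patients not yet discharged.
- Reconcile section 2 with Patient Selection Criteria and section 10 on whether randomisation precedes the preoperative visit.

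Outside the fix: body weight (unless a weight from before drinking was recorded), quadriceps strength, pain VAS and event outcomes.

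Cost: SAP wording and one degree of freedom per comparison (128 to 127), about half a point of power if the correlation is zero. No new measurement is needed where the recorded dates qualify.
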